Aim 1. To determine the technical failure rate of LFAs performed on nasal swabs and compare this to the failure rate of combined nasal and throat RT-PCR. Reasons for LFA test failure will be reviewed, with recommendations for training or improvements to be made before proceeding to the second stage.

Aim 2. To compare the acceptability of both RT-PCR and nasal swab LFAs using parental, and when appropriate child, feedback on the acceptability of both tests using a Likert Scale assessment of discomfort during collection of the test specimens.

Aim 3. To determine how many paired tests of RT-PCR and LFA need to be performed to assess for non-inferiority of LFA for all patients.

5. Rationale for this work:

As the prevalence of COVID-19 rises once again in the UK, the need for effective testing strategies is essential. Whilst combined nasal and throat RT-PCR currently remains the gold standard diagnostic test, alternative testing modalities may provide benefits which cannot be realised using RT-PCR. Point of care testing has the potential to rapidly identify infective patients which may improve the management of the patient and enable better protection of staff. The first part of the work described involves 'troubleshooting' the test in two pilot sites. This will enable identification for causes of test failure and enable the discomfort of both tests (nasopharyngeal swabbing and nasal swabbing) to be assessed. The evaluation will then go on to identify specific clinical processes which could be impacted most significantly by the introduction of LFA:

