Pre-operative screening: Prior to an elective procedure occurring a child currently undergoes a routine combined nasal and throat swab for RT-PCR. This has a very good diagnostic sensitivity and specificity for SARS-CoV-2 and can detect SARS-CoV-2 in children who have started shedding the virus but who are not yet symptomatic. However, a small proportion of children will have been infected with the virus but still be in the early incubation period at the time of the swab. In this situation, the swab will be negative for SARS-CoV-2 as the virus is not being shed, but there is the potential for shedding to commence between the time of the swab and the time of the procedure. If this were to occur, the person would have become potentially infectious to others. By 24 hours after a swab has been taken in people who are incubating the virus, 20% of those people will be shedding the virus and therefore be infectious. By 72 hours, just over 50% of those people will be shedding the virus. As LFA becomes substantially more sensitive as a test for individuals who are infectious, it is reasonable for it to be performed at the time of attending for surgery to assess for infectivity of the individual. This may impact on the service in several ways. Firstly, the availability of LFA may mean that the time between the combined nasal and throat RT-PCR swabbing and the procedure can be more safely limited to 72 hours, rather than the current 'best practice' recommendation which is that

swabbing is performed within 24 hours of the procedure whenever possible during times of high ($\geq 2\%$) prevalence. This will allow more 'give' in the system and potentially make access to services more equitable. Secondly, assessment of infectivity just before a high-risk AGP is planned to be performed, could affect care in two ways; Firstly, it may be decided by the clinicians, family, or both, to delay a case when the LFA is positive, as would occur if the nasopharyngeal swab was positive and it was clinically appropriate to defer the procedure. Secondly, if the case went ahead, airborne PPE would be worn by theatre staff in-line with Public Health England guidance for 'amber' and 'red' pathways(6). To validate the LFA results, a second nasopharyngeal swab would be taken when the patient is anaesthetised to limit discomfort of the repeated procedure.

Acute new admissions of children with symptoms which are in keeping with COVID-19:

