Children will undergo an additional swab which will be taken from the anterior nose prior to the routinely performed combined nose and throat swab being taken.

Prior to performing the anterior nasal swab, any nasal mucous will be removed by wiping or blowing the nose and then a swab the size of a cotton bud will be rubbed on the inside of the nose, below the level of the inferior turbinate to a maximum of 2.5cm. It will be rolled 5 times along the mucosa inside each nostril. This may tickle or cause some children to sneeze but is very unlikely to be painful. There is a risk of the

swabbing causing a nosebleed, but this is no more likely to occur than during other routine swabs that are currently taken in clinical practice for surveillance of other infections such as Methicillin-resistant *Staphylococcus aureus* (MRSA).

Children attending for an elective procedure currently routinely undergo combined nose and throat swabbing a few days before their procedure. If they are participating in the study they will be offered the opportunity to have an anterior nasal swab taken at the time of their pre-operative swab and at the time of admission for their elective procedure. To enable a comparison of the anterior nasal swab taken at admission with RT-PCR, an additional combined nose and throat swab will be taken whilst the child is anaesthetised.

Timeline

This pilot study will be undertaken in two sites - Alder Hey Children's Hospital, Royal Manchester Children's Hospital.

Study process (Participant):

After a child, their family or both, have agreed to participate in the study they will undergo an anterior nasal swab. The routine combined nose and throat swab can then be taken. For children who are undergoing nasal swabbing at the time of admission for a procedure, their additional combined nose and throat swab will be performed when they are anaesthetised.

A child who has multiple subsequent routine combined nose and throat swabs could be included in the study for each swab.

The family will be informed of the results at the time, if they wish to know them.

[figure not shown]
Study process (Recruiting healthcare worker, part of the direct care team):

The anterior nasal swab prior to the routine combined nose and throat swab. It will be rolled 5 times on the inside of each nostril to ensure that mucous and cells are collected.

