SARS-CoV-2 positive who have undergone surgery do not appear to have experienced significant adverse effects(7). However, discussion between the family, anaesthetic and surgical team is appropriate, and it may be decided to delay the procedure until a later date. If this occurs, it is recommended that the child undergoes a second nasopharyngeal swab to confirm the result and that they follow government advice on isolation.

If a child who is being newly admitted or is currently an inpatient has a positive lateral flow result, the family should be informed and if appropriate, household members should isolate in line with government guidance until the RT-PCR result is returned. Healthcare professionals caring for the patient should be meticulous in their use of appropriate PPE.

Clinical and Salivary Data Collection(8):

Written consent to participate: Y/N

If N - please record patient's reasons or concerns:

Recruiting Centre:

First 3 letters of postcode:

Local Hospital Number

Sex

Age (d) (m) (y)

Symptoms and duration (d)

Fever

Cough

Shortness of breath

Wheeze

Runny nose

Sore throat

Ear ache

Lethargy

Off feeds / reduced oral intake

Myalgia
Abdominal pain
Vomiting
Diarrhoea
Rash
Headache
Seizures
Reduced consciousness
Asymptomatic

Patient group:

Elective admission for surgery or diagnostic procedure
Diagnostic swab due to clinical suspicion of COVID-19 - New admission from ED
Screening swab for current inpatient

Date of Lateral flow antigen test:

Time of nasal swab collection:

Lateral flow assay result: positive / negative / test failure

Date of lateral flow assay result:

Time of lateral flow assay result:

If test failure, reason for failure:

Absent control line
Unable to confidently differentiate whether result line is present or absent
Other, Details:
Unknown

Photograph of lateral flow assay:

Parental assessment of the level of discomfort of the nasal test: /10
Parental assessment of the level of discomfort of the nasopharyngeal test: /10
Child assessment of the level of discomfort of the nasal test: /10
Child assessment of the level of discomfort of the nasopharyngeal test: /10

Nasopharyngeal RT-PCR swab result:

Date swab result returned:

Time swab result returned:

Results of swab: SARS-CoV-2 detected / SARS-CoV-2 not detected

Cycle threshold of RT-PCR if positive:

9. Outcome measures

As a pilot study there is not a single primary outcome measure. The followings measures will be assessed:

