Failure rates for LFA and RT-PCR will be described using percentages.

Reasons for LFA test failure will be described and where possible the reasons for this will be elicited by examining for correlation between the presence of symptoms (e.g. runny nose) and age.

Time from Sample acquisition to result for both lateral flow assay and RT-PCR.

Child reported Likert scale score for discomfort from each test. The results will be tested for normality and if normally distributed compared using student t test and if non-parametric will be compared using Mann-Whitney U test. The same will be performed for parental Likert scale scores.

Reasons for people refusing to participate will be described.

Concordance between results RT-PCR and LFA tests will be assessed in the following manner;

	LFA - Positive	LFA - Negative
RT-PCR: Positive		

RT-PCR - Negative		
--------------------------	--	--

Power calculations will be undertaken to determine the number of tests that need to be performed to determine non-inferiority of LFA compared to RT-PCR. Variations in prevalence levels, age, sex and cycle threshold will be considered within this calculation.

10. Data Management

Patient data will be collected in paper format in the departments where lateral flow assays are being undertaken. These will be transferred to the study team to perform the follow-up data collection. Data will be sent from Royal Manchester Children's Hospital to the Alder Hey study team in an anonymised format at the end of the pilot study period. Data will be transferred from an nhs.net/nhs.uk email address only and will be held on hospital databases. Anonymised data will be shared with Public Health England to enable rapid policy decisions to be made.

11. Approvals required for this work

The work described in this protocol will be undertaken following Research and Ethics Committee review. Sponsorship will be provided by Alder Hey Children's Hospital.

12. Dissemination

Anonymised results of this work will be shared with Public Health England. The results will be used to design a full study to assess the validity of LFA compared to RT-PCR.

13. Funding

The lateral flow antigen tests will be provided by Public Health England. Tests and machine readers will be provided free of charge to participating hospitals in exchange for data submission. Test and trace will provide funding for two full-time research nurses for both centres for two weeks

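### Aim 2 does not say how to treat the combined swab taken under anaesthesia, so the discomfort comparison could include a swab the child did not feel

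*Combined protocol and SAP*

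**What the plan says.** **When the swabs are taken.** Section 8 (Procedures) offers elective participants an "anterior nasal swab taken at the time of their pre-operative swab and at the time of admission for their elective procedure". For the admission nasal swab, the RT-PCR comparator is obtained as follows: "an additional combined nose and throat swab will be taken whilst the child is anaesthetised". The participant process in the same section repeats this: "their additional combined nose and throat swab will be performed when they are anaesthetised". Section 5, on pre-operative screening, gives the reason: "a second nasopharyngeal swab would be taken when the patient is anaesthetised to limit discomfort of the repeated procedure".

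**What is measured.** Aim 2 (Section 4) compares the acceptability of the two tests "using a Likert Scale assessment of discomfort during collection of the test specimens". The data collection list in Section 8 has four discomfort items, one each from parent and child for each swab. The two for the comparator are "Parental assessment of the level of discomfort of the nasopharyngeal test: /10" and "Child assessment of the level of discomfort of the nasopharyngeal test: /10". I read nasopharyngeal here as the combined nose and throat swab, since Section 5 uses that word for the same admission swab.

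**How it is analysed.** Section 9 lists "Child reported Likert scale score for discomfort from each test", to be compared by Student's t test or the Mann-Whitney U test according to normality. Parental scores are handled in the same way. Nothing in Section 4, 8 or 9 mentions anaesthesia in connection with these scores.

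**The concern.** Aim 2 asks how uncomfortable each swab is while it is being taken. An anaesthetised child has no such experience to report, and the protocol uses anaesthesia at this occasion precisely to spare the child discomfort. A score for that swab therefore does not measure what Aim 2 is about, while the nasal swab on the same occasion is taken at admission and does.

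Acceptability is one of three aims and part of the first research question, and it has a formal test. Results are to be shared with Public Health England (Sections 10 and 12). If scores from the anaesthetised swab enter the comparison, the combined swab looks gentler than it is for an awake child.

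The problem may also be hard to undo. The data collection list has a single elective category covering both the pre-operative and the admission occasion. It records when the nasal swab was collected, but for the combined swab only when the result came back. The form alone would not show which combined swabs were taken under anaesthesia.

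**Working it through.** The protocol gives no sample size, expected score, standard deviation or group sizes for the discomfort comparison, so there is no figure to reproduce. The check has three parts.

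**1. What the text allows.** There are two ways to complete the form for the anaesthetised swab, and the protocol rules out neither.

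- *A score is entered.* It is most plausibly given by a parent and is near zero. It joins the combined-swab scores in Section 9.
- *The item is left blank.* Both planned tests treat the two swabs as independent samples. The admission nasal score therefore still enters on one side, with no partner on the other.

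**2. Size if zeros are entered.** Assumptions, none from the documents: awake combined mean 6, awake nasal mean 3, every anaesthetised swab scored 0. Let p be the share of pairs with an anaesthetised combined swab.

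- Combined mean = 6 × (1 − p)
- Difference = 6 × (1 − p) − 3

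| p | Combined mean | Difference |
|---|---|---|
| 0 | 6.0 | 3.0 |
| 10% | 5.4 | 2.4 |
| 25% | 4.5 | 1.5 |

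Varying the assumed awake combined mean, with the nasal mean kept at 3:

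- Mean 5: the difference goes from 2.0 to 5 × 0.90 − 3 = 1.5 at 10%, and to 5 × 0.75 − 3 = 0.75 at 25%.
- Mean 7: it goes from 4.0 to 7 × 0.90 − 3 = 3.3 at 10%, and to 7 × 0.75 − 3 = 2.25 at 25%.

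The direction is the same throughout, because each zero lowers the combined mean only.

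*Which p is plausible?* Suppose a fraction e of children are elective and all of them give both a pre-operative and an admission pair, while every other child gives one pair. Then p = e / (1 + e). This gives p = 10% at e = 1/9 and p = 25% at e = 1/3. Lower uptake at admission reduces p. So do repeat inpatient swabs, which Section 8 permits. The protocol states neither e nor uptake.

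**3. Size if blanks are left.** With N occasions there are N nasal scores and N × (1 − p) combined scores. Unequal numbers alone do not bias either test. Let d be the amount by which admission nasal scores differ on average from other nasal scores. The pooled nasal mean moves by p × d. If d were 1 point (assumed), that is 0.10 at 10% and 0.25 at 25%. If d = 0, there is no shift.

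**The case against.** The strongest reply is that the protocol never says this swab is scored. The discomfort items appear once in the list, and nothing says they are completed on each occasion. The repeat-inclusion rule in Section 8 refers to routine combined swabs, whereas the anaesthetised one is called additional, and its stated purpose is comparison with RT-PCR, not acceptability. Aim 2 also asks for child feedback only where that is suitable, which gives staff room to omit it. All of this stands. The point is an ambiguity, not a stated plan to pool. The qualifier in Aim 2 narrows the gap without closing it, because it covers the child's feedback and not the parent's, and Section 9 does not carry it forward.

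Several stronger readings are tempting, and the documents do not support them:

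- *That the discomfort advantage could vanish.* With the assumed means of 6 and 3, the difference reaches 0 at p = 50%. By the formula above this needs e = 1: an all-elective sample, full uptake at both occasions and every score zero. Any child from the other two groups lowers p.
- *That blanks bias the result in themselves.* They do so only if admission nasal scores differ systematically from the others, and the documents give no evidence either way.
- *That the admission nasal scores are worthless.* That swab is taken at admission and its scores are valid. They only lack a comparable partner.
- *That sedated intensive care children must be excluded too.* The protocol does not discuss sedation at swabbing, so the point does not extend to them.

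It is also fair to say that zeros would work against the nasal swab and so would not falsely favour the new test, that no decision threshold is attached to discomfort, and that this is a pilot without a single primary outcome. These limit the consequences. They do not make a score from an anaesthetised child a measure of discomfort.

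**Conclusion.** The point holds as a gap in the specification. The protocol places one combined swab under anaesthesia to limit discomfort, then collects and compares discomfort for each test without saying what happens to that swab. Scores near zero would understate the nasal swab's advantage. Blanks would leave unmatched nasal scores in an unpaired comparison, with a smaller and conditional effect.

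The size cannot be determined from the documents. The loss of 0.6 points at 10% of pairs (3.0 to 2.4) and 1.5 points at 25% (3.0 to 1.5) rests wholly on the assumed means and on every anaesthetised swab being scored 0. It shows direction and order of magnitude only. The awake pre-operative pairs from elective children, and pairs from the other groups, are not affected by this point. The change should be made before data collection, because the form would not identify the affected pairs afterwards.

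**What to change.** 1. **Section 9:** state that the Aim 2 comparison, for child and parent scores alike, uses only occasions on which both swabs were taken without anaesthesia. Analyse these as within-child pairs, with a paired t test or Wilcoxon signed-rank test in place of Student's t or Mann-Whitney U.
2. **Data collection list, Section 8:** add an option 'not applicable - anaesthetised' to both discomfort items for the combined swab. This also marks the affected occasions.
3. **Reporting:** summarise the admission nasal-swab scores separately and descriptively.

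The cost is a sentence or two in Section 9 and one option on the form, with no change to when or how any swab is taken. The downside is that admission nasal scores, valid in themselves, leave the formal comparison, which then rests on fewer observations.

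### Aim 1 promises a comparison of LFA and RT-PCR failure rates, but Section 9 plans two percentages without intervals, and the data form has no category for an RT-PCR failure

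*Combined protocol and SAP*

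**What the plan says.** Section 4, Aim 1, is to determine the LFA technical failure rate and "compare this to the failure rate of combined nasal and throat RT-PCR". It adds that reasons for LFA failure will be reviewed, and training or improvements recommended, before a second stage.

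Section 9 gives one sentence of analysis for the rates: "Failure rates for LFA and RT-PCR will be described using percentages". It then plans to describe the reasons for LFA failure and examine them against symptoms and age. The same section opens with "As a pilot study there is not a single primary outcome measure".

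The design is set out under the Procedures heading of Section 8 as follows: "Children will undergo an additional swab which will be taken from the anterior nose prior to the routinely performed combined nose and throat swab". At elective admission, the nasal swab is matched with a further combined swab under anaesthesia. Repeat entries are allowed: "A child who has multiple subsequent routine combined nose and throat swabs could be included in the study for each swab".

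The data list at the end of Section 8 has, for the LFA, "Lateral flow assay result: positive / negative / test failure", followed by reasons for failure. For RT-PCR it has "Results of swab: SARS-CoV-2 detected / SARS-CoV-2 not detected".

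No sample size is stated. The only indication of scale is in Section 13: "Test and trace will provide funding for two full-time research nurses for both centres for two weeks".

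**The concern.** An aim worded as a comparison needs a planned quantity that answers it. Here the natural one is the difference between two failure proportions observed on the same swabbing occasions, with an interval. Section 9 plans neither the difference nor an interval, and its concordance table has only positive and negative cells, so failed tests fall outside it. Section 9 does name a comparison method for the discomfort scores, so comparative analysis was not ruled out for the pilot as a whole.

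The data form adds a more basic problem. Without a category for a failed, invalid or missing RT-PCR, one of the two percentages cannot be calculated as planned.

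Anonymised data go to Public Health England for rapid policy decisions (Section 10), and the results will be used to design a full study (Section 12). If the pilot is small, two bare percentages could make a chance gap look like a real shortfall of the LFA. A count of zero could likewise be read as a test that does not fail.

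**Working it through.** **Inputs from the documents.** Aim 1 calls for a comparison. Section 9 specifies percentages only. The tests are paired within an occasion and may be repeated within a child (Section 8). Failure is recorded for the LFA but not for RT-PCR (Section 8). There is no sample size, expected failure rate or precision target for Aim 1, so there is no planned figure to reproduce.

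**Step 1: can the RT-PCR percentage be computed?** The LFA field has three outcomes, one of which is failure. The RT-PCR field has two, neither of which is failure. A blank RT-PCR entry could mean an invalid result, an inadequate specimen, a swab not taken or a result not returned. No definition separates these, so the RT-PCR numerator is not collected as listed.

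**Step 2: how wide is the uncertainty on the difference?** The values of n and the rates below are assumptions. Let p1 and p2 be the LFA and RT-PCR failure rates, p11 the proportion of pairs in which both fail, b = p1 − p11, c = p2 − p11 and d = p1 − p2. The 95% half-width is 1.96 × √[(b + c − d²)/n].

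For n = 100, p1 = 0.05, p2 = 0.01, d = 0.04:
- Independent failures: p11 = 0.0005, b = 0.0495, c = 0.0095. Half-width = 1.96 × √[(0.0590 − 0.0016)/100] = 4.7 points. This equals the unpaired result, since 0.05 × 0.95 + 0.01 × 0.99 = 0.0574.
- Maximal overlap: p11 = 0.01, b = 0.04, c = 0. Half-width = 1.96 × √[(0.0400 − 0.0016)/100] = 3.8 points.

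The range, from maximal overlap to independence, for other assumed values:

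| Pairs | 5% v 1% (difference 4 points) | 10% v 2% (difference 8 points) |
|---|---|---|
| 50 | 5.4 to 6.6 | 7.5 to 9.2 |
| 100 | 3.8 to 4.7 | 5.3 to 6.5 |
| 200 | 2.7 to 3.3 | 3.8 to 4.6 |
| 400 | 1.9 to 2.4 | 2.7 to 3.2 |

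**Step 3: one worked data set (assumed).** Take 100 pairs with 5 LFA-only failures, 1 RT-PCR-only failure, none shared and 94 with neither.
- Exact (Clopper-Pearson) 95% intervals: 5/100 gives 1.6% to 11.3%; 1/100 gives 0.03% to 5.4%.
- Newcombe paired difference: 4.0 points, 95% CI −1.3 to 10.2.
- The same interval with the correlation set to zero: −1.3 to 10.2.
- Exact McNemar test: p = 0.22. Unpaired Fisher test: p = 0.21.

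Section 9 would report this as 5% and 1%.

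**Step 4: zero failures.** The upper limit of the exact two-sided 95% interval is 1 − 0.025^(1/n): 7.1% for n = 50, 3.6% for n = 100 and 1.8% for n = 200.

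**Step 5: what does pairing contribute?** At 5% v 1% and n = 100, the most that overlap can save is 1 − 3.84/4.70 = 18% of the half-width. It matters more when the rates are similar: at 5% v 5% and n = 100, the half-width falls from 6.0 points under independence to 4.4 when half the failures are shared.

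**The case against.** The best defence is that this is a short pilot with no primary outcome, and descriptive reporting is normal in a pilot. If counts and denominators are published, anyone can compute intervals later. That stands as an argument against requiring a hypothesis test. It does not cover the gap in full: Section 9 promises percentages rather than counts, separate totals do not give the pair-by-pair table, and an RT-PCR failure that was not recorded cannot be recovered from the form.

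Three stronger readings are tempting, and the documents do not support them.

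- *That the failure-rate comparison gates the second stage.* Aim 1 ties the step before the second stage to a review of why LFA tests failed, with recommendations. No threshold or go/no-go rule rests on the rates or their difference.
- *That the pilot would yield no estimate of the difference.* If both percentages were available, subtraction would give one. What is missing is its uncertainty and, as the form stands, the RT-PCR percentage itself.
- *That ignoring the pairing distorts the result.* Section 9 names no method for this outcome, so it does not name a wrong one. In the worked data set, the paired and unpaired intervals agree to the decimal shown.

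Nor can it be taken as fact that failures will be few. Section 5 notes that failure may be more common in children with rhinorrhoea, and symptomatic admissions are one of the three groups recruited.

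**Conclusion.** The point holds as a mismatch between a stated aim and its analysis, together with a gap in data collection. The collection gap needs closing first, because without it Aim 1 cannot be answered from the form as listed. Once it is closed, most of the gain comes from attaching intervals, and respecting the pairing is a smaller benefit.

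The size depends on numbers the protocol does not give. Under the assumed rates, the half-width is close to or larger than the difference at 50 to 100 pairs for 5% v 1%, and at 50 pairs for 10% v 2%. By 400 pairs it is well below the difference in both cases. These half-widths treat pairs as independent; repeat swabs from one child may make the true intervals wider.

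The change is worth making before recruitment. It does not put the pilot's overall design in question.

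**What to change.** 1. In the Section 8 data list, add a third outcome to the RT-PCR result covering test failure, an invalid result or a specimen not obtained, and define what counts as each.

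2. Replace the failure-rate sentence in Section 9 with:

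> Failure counts and denominators will be reported for each test and cross-tabulated by pair (LFA failed yes/no by RT-PCR failed yes/no). Each rate will be given with a 95% CI, and the LFA minus RT-PCR difference with a paired 95% CI (for example Newcombe or Tango), using resampling by child or a cluster-robust interval where children contribute more than one pair.

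A significance test such as McNemar is optional. The cost is one extra category on the form, its definition and a little more analysis. No additional swabs or participants are needed.

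### The Aim 2 discomfort scores are paired by child, but the plan names Mann-Whitney U, a test for independent groups, for non-normal scores and gives no rule for repeat pairs

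*Combined protocol and SAP*

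**What the plan says.** Section 4, Aim 2, compares the two tests "using parental, and when appropriate child, feedback on the acceptability of both tests using a Likert Scale assessment of discomfort".

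Section 8, Procedures, gives both swabs to the same child: "Children will undergo an additional swab which will be taken from the anterior nose prior to the routinely performed combined nose and throat swab". The data collection form in section 8 has four discomfort items: a parent score and a child score for each swab. The last of them reads "Child assessment of the level of discomfort of the nasopharyngeal test: /10".

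Section 9 (Outcome measures) tests the scores for normality and then chooses the comparison: "if normally distributed compared using student t test and if non-parametric will be compared using Mann-Whitney U test". Parent scores are to be handled in the same way. No paired method is named anywhere in the document.

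On repeats, section 8, Study process (Participant), says: "A child who has multiple subsequent routine combined nose and throat swabs could be included in the study for each swab". Under Consent, one inpatient consent lasts for the two weeks of the study. Elective children are offered a nasal swab "at the time of their pre-operative swab and at the time of admission for their elective procedure"; the combined swab that accompanies the second of these is taken under anaesthesia. The document does not say how several pairs from one child are to be analysed.

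**The concern.** The design makes each child his or her own control. A Mann-Whitney U test treats the nasal and combined scores as coming from two unrelated sets of children. It discards the pairing, and its standard error is wrong whenever the two scores are correlated. Integer scores bounded at 0 and 10 are often skewed, so this branch may well be the one used.

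The t test branch is different. Student's t test exists in paired and unpaired forms and the text does not say which is meant, nor whether normality is checked on the differences or on the two sets of scores.

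Two related gaps bear on the same comparison. A child swabbed repeatedly contributes correlated differences, so correcting the test without a rule for repeats would exchange one error for another. And a pair made of an awake nasal swab and an anaesthetised combined swab does not compare like with like.

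At stake is one of the three aims, and the only comparison for which section 9 names a test.

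**Working it through.** The document gives no sample size, SD, within-child correlation or repeat frequency for Aim 2, so there is no figure to reproduce. Everything below is illustration.

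**Assumed inputs.** Two-sided 5% level; 50 pairs; SD of each score 2.5; within-child correlation ρ of 0.3, 0.5 or 0.7.

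**Step 1. One pair per child: type I error.** The true variance of the mean difference is (1 − ρ) times the variance an unpaired test assumes. The unpaired standard error is therefore too large by k = 1/√(1 − ρ), and the real type I error is 2 × (1 − Φ(1.96k)).

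| ρ | k | Unpaired, normal approximation | Mann-Whitney, simulated |
|---|---|---|---|
| 0.3 | 1.20 | 1.9% | about 2% |
| 0.5 | 1.41 | 0.6% | about 1% |
| 0.7 | 1.83 | 0.03% | about 0.1% |

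The simulations used scores rounded and limited to 0–10. The signed-rank test stayed near 5% throughout.

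**Step 2. One pair per child: power.** SE = 2.5 × √(2(1 − ρ)/50) = 0.418, 0.354 and 0.274. Unpaired power is Φ(d/SE − 1.96k); paired power is Φ(d/SE − 1.96).

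For d = 1 point:

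| ρ | Unpaired, formula | Paired, formula | Mann-Whitney, simulated | Signed-rank, simulated |
|---|---|---|---|---|
| 0.3 | 51.9% | 66.7% | about 48% | about 62% |
| 0.5 | 52.3% | 80.7% | about 48% | about 76% |
| 0.7 | 52.9% | 95.5% | about 48% | about 92% |

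For d = 2 points, unpaired power by formula is 99.3, 99.8 and 99.99%. Simulated Mann-Whitney power is above 98% in every case.

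**Step 3. Repeat pairs under a corrected test.** Suppose 20% of children give two pairs and the rest one, with t the intraclass correlation (ICC) of the differences. The design effect is D = (0.8 + 0.4(1 + t))/1.2. A paired test that ignores the repeats has type I error 2 × (1 − Φ(1.96/√D)).

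| t | D | Type I error |
|---|---|---|
| 0.3 | 1.10 | 6.2% |
| 0.5 | 1.17 | 7.0% |
| 0.7 | 1.23 | 7.8% |

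In simulation at t = 0.5, using the first pair only gave 4.6 to 5.3%, and generalised estimating equations (GEE) clustered by child gave 5.4 to 5.7%.

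**Step 4. Repeat pairs under Mann-Whitney.** Repeats and lost pairing act in opposite directions. In the same scenario, with k = 1/√((1 − ρ)D) and t = 0.5, the unpaired type I error is 3.0, 1.0 and 0.09%, still conservative. Heavier repetition can reverse this. At ρ = 0.3 and t = 0.7, with 20% of children giving three pairs, D = (0.8 + 0.6 × 2.4)/1.4 = 1.6, (1 − ρ)D = 1.12, and the error is 6.4%. No general claim that the unpaired test stays below 5% is safe.

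**The case against.** The best defence is that little depends on this test. The study is a pilot without a single primary outcome, no decision rule or sample size rests on the p-value, the error with single pairs is conservative, and a large difference would be found either way. The raw pairs stay on the form, so a careful analyst could run the right test. All of that stands, and it bounds the importance of the point. It does not make Mann-Whitney U suitable for paired data.

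Four stronger readings are tempting, and the document does not support them.

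- *Every Aim 2 p-value will be wrong.* Only the Mann-Whitney branch is definitely wrong; a paired t test is compatible with the text.
- *The scores are certainly paired within one parent.* The form does not say that the same parent rates both swabs. Pairing by child is certain; pairing by parent is inferred.
- *Repeats will be widespread.* The sentence on repeat entry concerns routine combined swabs, whereas the anaesthetised swab is an added one. Once pairs with an anaesthetised swab are set aside, an elective child would normally give one awake pair, so the issue is mainly inpatients over two weeks. The only frequency mentioned is weekly screening on transplant wards in many units (section 5); the frequency at the two sites is not given.
- *Repeats cannot be linked.* Manchester data go "to the Alder Hey study team in an anonymised format at the end of the pilot study period", but the document does not say that they will lack a study code, and the form carries the "Local Hospital Number".

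**Conclusion.** The point holds as a definite but bounded error of method. For non-normal scores, section 9 prescribes an independent-samples test for data paired by child; for normal scores, it leaves the pairing open.

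If the Mann-Whitney branch is used with one pair per child and positive correlation, the cost is power. The practical risk is missing a modest difference of about 1 point, not claiming a false one. The mean difference from complete pairs is unaffected. The missing repeat rule is a second gap, and it matters most once the test is corrected, because the error then becomes anti-conservative.

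The sizes rest on assumed values for the number of pairs, SD, correlation, ICC and share of children repeating. The direction of each effect needs only positive correlation. The consequence is confined to the acceptability result. It should be fixed, but it does not threaten the rest of the pilot.

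**What to change.** Replace the sentence on the test in section 9 with:

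> Within-child differences (combined swab minus nasal swab) will be analysed separately for child and parent scores by paired t test or Wilcoxon signed-rank test, with the mean or median difference and 95% CI; any normality check applies to the differences. If a child has more than one awake pair, a mixed model or GEE of the differences clustered by child will be used. Pairs whose combined swab was taken under anaesthesia are excluded from this comparison.

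A simpler alternative for the second sentence is to use only each child's first awake pair. The clustered model is closer to the protocol's intention to include a child for each swab.

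Optional: keep a child-level study number in the anonymised data, and add a tick box to the form for combined swabs taken under anaesthesia, so that repeats and such pairs can be identified. With the first-pair rule, each site could instead make the selection from the hospital number already on the form.

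The cost is a few sentences of protocol wording and, if adopted, one identifier and one tick box. No extra patients or procedures are needed.
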